8.2 Surveys (Appendices 2 to 7)

8.2.1 Baseline surveys to be completed are:

1. COH-QOL-CRC (full survey; Appendix 2a AND Appendix 2b)
2. HADS (Appendix 3)
3. PAM (Appendix 4)
4. Self-Efficacy (Appendix 5)
5. Ostomy Knowledge (Appendix 6)
6. Burden of Care (full survey; Appendix 7a [NOTE: **Do not include** Greatest Challenge portion of Appendix 7a])
7. Goal Setting (page 1 of 4; Appendix 10)

8.2.2 End of Session surveys to be completed are:

1. COH-QOL-CRC (43 scaled items only; Appendix 2b)

2. HADS (Appendix 3)
3. PAM (Appendix 4)
4. Self-Efficacy (Appendix 5)
5. Ostomy Knowledge (Appendix 60)
6. Burden of Care (short form; Appendix 7b)
7. Goal Setting (pages 2 and 3 of 4; Appendix 10)

8.2.3 6-month Follow-up surveys to be completed are:

1. COH-QOL-CRC (43 scaled items only; Appendix 2b)
2. HADS (Appendix 3)
3. PAM (Appendix 4)
4. Self-Efficacy (Appendix 5)
5. Ostomy Knowledge (Appendix 6)
6. Burden of Care (full survey; Appendix 7a [NOTE: **Include** Greatest Challenge portion of Appendix 7a])
7. Goal Setting (page 4 of 4; Appendix 10)

8.2.4 **RedCap® Surveys.** Surveys will be available to complete electronically via the web in RedCap, which will be preferred administration method unless subjects cannot manage the method or express a strong preference against it. The UA Data Core will provide each medical center with a list of survey ID's linked to subject IDs. The survey ID's allow the subject to log into the RedCap survey and can only be used once. Medical centers will provide each subject with the survey link and his or her survey ID at the appropriate time for each of the three survey periods.

8.2.5 **Survey Tracking.** Survey/Participant status will be tracked using an MS Access tracking database maintained at UA Data Core, with mirror databases at each medical center for their respective samples. However, the medical center tracking database will account for all potentially eligible participants, whereas the UA Data Core tracking database will only contain consented subjects. Since paper surveys are returned to respective sites, whereas RedCap surveys are transmitted to UA Data Core, the disposition of consented subjects in the master tracking database will be synchronized with the medical center tracking databases on a weekly basis.

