The COH QOL-CRC assesses ostomy burden and care abilities, including time taken to perform daily ostomy care, comfort with ostomy care, comfort with diet, adjustment of diet for ostomy, appetite, clothing and other problems with ostomy placement. We will also measure clinically related outcomes, including medical attention for problems with bowel, bladder, or ostomy. Changes in these responses will be compared between treatment groups with linear mixed models, chi-square tests or t-tests, as appropriate.

Descriptive statistics will be presented on attendance at training sessions. We will describe and contrast quantity and type of ostomy-care help (professional and lay) sought outside of the training sessions, including calls for support from study Peer Ostomates. Self-reported Peer Ostomate call frequency and duration will be corroborated with a call log maintained by the Peer Ostomate. We will evaluate hypothesized association between OSMT attendance level and outcomes using linear mixed models that have a weighted attendance score as an independent variable. Alternative attendance scores will be tested that give weight to ostomy-care help outside of training sessions.

12.3 Aim 2: Determine the differences in ostomy-related **medical care utilization** and family **financial burden** imposed on survivors between OSMT and UC groups.

Hypothesis 2.1: OSMT telehealth subjects will use fewer **ostomy-specific** family resources in the 6 months after OSMT compared to UC subjects.

Hypothesis 2.2: OSMT telehealth subjects will use fewer **ostomy-specific** health care services in the 6 months after OSMT compared to UC subjects.

Question 2.1: What is the difference in the overall levels of **ostomy-related** family financial burden between OSMT and UC groups?

Question 2.2: What are types and levels of effort of OSMT intervention personnel and specific equipment, supplies, and informatics support required to implement and operate a successful OSMT program; what are participants' levels of use of ostomy-specific health care

services and supplies; and what are the time and in-home requirements for participating in OSMT for survivors and their family caregivers. This information is required for replicating our OSMT intervention in the event that we find it improves the primary and secondary outcomes of OSMT participants.

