15.7 Appendix 7a Burden of Ostomy Care Survey (full survey, baseline and followup)

BURDEN OF OSTOMY CARE

This study aims to collect data on the burden associated with families' use of ostomy care and supplies, including ostomy-related medications, ostomy-related health care visits, travel costs to obtain ostomy-related care and supplies, and time spent on ostomy management tasks. We ask that you please answer these questions while thinking specifically about the burden of ostomy-related care. This is not a test; please give us your best estimates based on your personal experience.

1. What kind of Ostomy do you have? Colostomy Ileostomy Urostomy Other

2. In-person Visits with Wound and Ostomy Care Nurse in the past 4 weeks:

- a. Did you visit a Nurse in person in the past 4 weeks (at a medical office, hospital, and/or in your home)? No (If NO, skip to Question 3. below.) Yes
- b. **If YES:** How many times did you visit the Nurse in the past 4 weeks? 1 2 3-4 5-8 More than 8

Please answer questions 2c through 2g thinking specifically about your most recent visit to the Nurse.

- c. How much do you typically pay out-of-pocket for each Nurse visit (copayments, deductibles, or other costs for the visit that weren't covered by your insurance)?
 Nothing \$1-\$10 \$11-\$25 \$26-\$50 \$51-\$75 \$76-\$100 \$101+
- d. Did you have to travel to see the Nurse for your most recent visit? No (If NO, skip to Question 3. below.) Yes
- e. How much do you typically pay out-of-pocket to get to and from each Nurse visit (such as the cost for taxi, bus, or parking)? \$1-\$5 \$6-10 \$11-15 \$16-\$25 \$26-\$50 \$51-\$100 \$101+
- f. Approximately how far did you have to travel to the Nurse Visit location? 1-4 miles 5-8 mi. More than 8 mi.
- g. Approximately how much time did it take you to get from your home to the Nurse Visit location? 1-10 mins 11-30 mins More than 30 mins

3. Telephone and/or email consultations with a Wound and Ostomy Care Nurse in the past 4 weeks:

- a. Did you have any telephone and/or web consultations with the Nurse in the past 4 weeks? No (If NO, skip to Question 4 below.) Yes
- b. **If YES:** How many telephone and/or web consultations have you had with a Wound and Ostomy Care Nurse over the past 4 weeks? 1 2 3-4 5-8 More than 8

Please answer Question 3c thinking specifically about your most recent telephone or web consultation with the Nurse.

- c. How much did you have to pay out-of-pocket for this Nurse consultation?

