 Nothing \$1-\$10 \$11-\$25 \$26-\$50 \$51-\$75 \$76-\$100 \$101+

4. In-person Visits with a Physician for stoma and/or bowel function problems in the past 4 weeks:

- a. Did you visit a Physician in person for stoma and/or bowel function problems in the past 4 weeks? No (If NO, skip to Question 5. below.) Yes
- b. **If YES:** How many times did you visit the Physician in the past 4 weeks?
 1 2 3-4 5-8 More than 8

Please answer Questions 4c through 4g thinking specifically about your most recent visit to the Physician.

- c. How much do you typically pay out-of-pocket for each Physician visit (copayments, deductibles, or other costs for the visit that weren't covered by your insurance)?
 Nothing \$1-\$10 \$11-\$25 \$26-\$50 \$51-\$75 \$76-\$100 \$101+
 - d. Did you have to travel to see the Physician for your most recent visit? No (If NO, skip to Question 5. below.) Yes
 - e. How much do you typically pay out-of-pocket to get to and from each Physician visit (such as the cost for taxi, bus, or parking)? \$1-\$5 \$6-10 \$11-15 \$16-\$25 \$26-\$50 \$51-\$100 \$101+
 - f. Approximately how far did you have to travel to the Physician visit location? 1-4 miles 5-8 mi. More than 8 mi.
 - g. Approximately how much time did it take you to get from your home to the Physician visit location? 1-10 mins 11-30 mins More than 30 mins
5. **What other sources do you use to find more information about your ostomy and daily care?** (Fill in all that apply)
 Internet Magazines Other people with an ostomy Support Group
 Other (please specify)
-
6. **If you wear a pouch and have encountered any problems with it, please explain below what those problems are/were?**
-
-
-
7. **How long was it before you felt comfortable with your daily ostomy care?**
 0 < 1 month 1-12 months 12+ months I am still not comfortable
8. **On average, how long does it take to do your daily ostomy care?**
 0-5 min 5-10 min 10-15 min 15-30 min 30-60min More than 60min
9. **Do you irrigate (flush) your ostomy?**
 Yes → Please answer 9a. I used to but stopped → Please answer 9b No Please skip to 10.
- 9a. **IF YES, How often do you irrigate your ostomy?** Once a day Every other day Every third day Other (please specify) _____
- 9b. **If you used to irrigate but stopped, why did you stop?** Pain Hernia Too time consuming
 Other (Please specify) _____
10. **Please describe the reasons you irrigate your ostomy.** (Check all that apply)

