15.7 Appendix 7b Burden of Ostomy Care Survey (short survey, after session completion)

BURDEN OF OSTOMY CARE: CHECK-IN REPORT

This study aims to collect information on families' use of ostomy care and supplies, including ostomy-related medications, and ostomy-related health care visits. We ask that you please answer these questions while thinking specifically about your *ostomy-related care*. This is not a test. Please give us your best estimates based on your personal experience.

1. In-person Visits with Wound and Ostomy Care Nurse in the past 4 weeks:

- a. Did you visit a Nurse in person in the past 4 weeks (at a medical office, hospital, and/or in your home)? No (**IF NO**, skip to Question 3. below.) Yes
- b. **IF YES:** How many times did you visit the Nurse in the past 4 weeks? 1 2 3-4
 5-8 More than 8

2. Telephone and/or email consultations with a Wound and Ostomy Care Nurse in the past 4 weeks:

- a. Did you have any telephone and/or web consultations with the Nurse in the past 4 weeks? No (**IF NO**, skip to Question 4. below.) Yes
- b. **IF YES:** How many telephone and/or web consultations have you had with a Wound and Ostomy Care Nurse over the past 4 weeks? 1 2 3-4 5-8 More than 8

3. In-person Visits with a Physician for stoma and/or bowel function problems in the past 4 weeks:

- a. Did you visit a Physician in person for stoma and/or bowel function problems in the past 4 weeks? No (**IF NO**, skip to Question 5. below.) Yes
- b. **IF YES:** How many times did you visit the Physician in the past 4 weeks?
 1 2 3-4 5-8 More than 8

4. What other sources do you use to find more information about your ostomy and daily care? (Fill in all that apply)

- Internet Magazines Other people with an ostomy Support Group
- Other (please specify)

5. If you wear a pouch and have encountered any problems with it, please explain below what those problems are/were?

6. Do you feel comfortable with your daily ostomy care? Yes No
7. On average, how long does it take to do your daily ostomy care?
 0-5 min 5-10 min 10-15 min 15-30 min 30-60min More than 60 min
8. How often do you typically discard a used bag and use a new bag?
 At every emptying Once a day Once every 2-3 days Less often
9. How often do you typically change your wafer on a typical week?
 1 2 3 4-7 More than 7
10. How much time does it usually take you to change your wafer and bag?
 1-15 minutes 16-30 minutes 30-45 minutes 45-60 minutes
 More than 60 minutes

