**Statistical Analysis Plan**

## Statistical Analysis Plan

**General.** Aim 1 will be analyzed with linear mixed models for repeated measures. Aim 2 will utilize a variety of sources and methods to enumerate the intervention program and ostomy-related family resources in each study arm.

**Aim 1:** Using our enhanced telehealth techniques, determine if **patient activation**, self-efficacy, ostomy-related knowledge, and HRQOL will be improved and sustained over time in the online interactive communication Ostomy Self-Management Telehealth program (OSMT) curriculum compared to a UC group.

Under an intent-to-treat approach, change in outcomes will be evaluated longitudinally with linear mixed models, testing the effect of study arm adjusted for potential confounders. Such models evaluate both associations and rates of change, accounting for within-subject correlation. The Primary Outcome will be PAM. Secondary Outcomes include SE, COH-QOL-CRC scales, and Ostomy Knowledge. Post hoc contrasts will evaluate effect of training (baseline to post) and whether effect is sustained after training (6 month post to follow-up). Standard multivariable modeling procedures will be used to select or eliminate potential confounding variables, starting with candidate variables that are biologically plausible or found to be associated with endpoint change scores (baseline vs. follow-up) in bivariate analyses with a p-value of less than 0.20. Potential candidate covariates and confounders include (but are not limited to) CG participation in training sessions, depression (HADS), time since surgery, ostomy type, age, sex, stage, anticipated permanence of ostomy, and pre- or post-surgical radiation or chemotherapy. We will explore potential interaction for plausible effect modifiers, such as gender, or having a CG.

The COH QOL-CRC assesses ostomy burden and care abilities, including time taken to perform daily ostomy care, comfort with ostomy care, comfort with diet, adjustment of diet for ostomy, appetite, clothing and other problems with ostomy placement. We will also measure clinically related outcomes, including medical attention for problems with bowel, bladder, or ostomy. Changes in these responses will be compared between treatment groups with linear mixed models, chi-square tests or t-tests, as appropriate.

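### Comfort with daily ostomy care is asked as past time to comfort at baseline and six months but as current yes/no after the sessions, so only a coarse, unspecified binary links the three surveys.

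*Protocol*

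**What the plan says.** Protocol 12.2 and the SAP carry the same text. Among the things assessed they list "time taken to perform daily ostomy care, comfort with ostomy care, comfort with diet", and they then say: "Changes in these responses will be compared between treatment groups with linear mixed models, chi-square tests or t-tests, as appropriate". Both attribute these responses to the COH-QOL-CRC. In the readable appendices, however, the questions on comfort with daily care are in the Burden of Ostomy Care survey.

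Protocol 8.2 assigns the full form (Appendix 7a) to baseline and six months, and the short form (Appendix 7b) to the end of the sessions. Question 7 of Appendix 7a reads "How long was it before you felt comfortable with your daily ostomy care". Its choices are under 1 month, 1-12 months, 12+ months, and "I am still not comfortable". Question 6 of Appendix 7b reads "Do you feel comfortable with your daily ostomy care", with yes or no. Neither document says how the two are to be put on one scale.

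**The concern.** A comparison of change needs the same quantity at each time. Here the middle survey records a present state, while the outer two mostly record a past event. Once a person has become comfortable, the correct answer to the 7a question is fixed. Later loss of comfort has no proper place on the form, because the fourth choice implies that comfort was never reached.

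Comfort with self-care is something the program sets out to improve, and six months is when durability is judged. If usual-care participants lost comfort more often than OSMT participants, the six-month form could miss that benefit. If a score were built from the time categories, part of what it measured would be date of surgery and memory.

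**Working it through.** The plan gives no expected rate, detectable difference or power for this item, so there is no figure to reproduce. The check is a comparison of the forms, followed by simple counts.

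**1. The forms side by side**

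| Survey | Question | Choices |
|---|---|---|
| Baseline | 7a Q7, time taken to become comfortable | <1 month; 1-12 months; 12+ months; still not |
| End of sessions | 7b Q6, comfortable now | yes; no |
| Six months | 7a Q7 again | as at baseline |

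Daily care time has the same question and choices on both forms (7a Q8, 7b Q7), so its change can be analysed directly. Comfort does not.

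**2. The only alignment available**

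Code still not as no and any time category as yes. With literal answers, the binary records the following:

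| True course | Baseline | End of sessions | Six months | Result |
|---|---|---|---|---|
| Never comfortable, gains comfort during sessions, keeps it | no | yes | yes | correct |
| Comfortable throughout | yes | yes | yes | correct |
| Comfortable, loses it during sessions, stays so | yes | no | yes | loss seen, then a false recovery |
| Comfortable, loses it after sessions | yes | yes | yes | loss missed |
| Once comfortable, lost it before baseline, stays so | yes | no | yes | false decline and false recovery |

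Some people in the last three rows may tick still not anyway. The form does not settle which answer is right.

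**3. The time categories as a score**

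Protocol 5.1 sets the first session at least six weeks after surgery, with no maximum. A person who becomes comfortable during the sessions is therefore already past one month. Someone a few months out moves from still not to 1-12 months; someone two years out with the same gain moves to 12+ months. On an ordered four-category score that is two steps against one, and the difference is time since surgery. For someone already comfortable at baseline, any change of category is recall error.

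**4. How many people can show improvement**

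Let q be the share still not comfortable at baseline and n the number per arm. The number who can improve is n × q. Protocol 4.0 reports that 18% in an earlier study needed a year or more or never became comfortable, so never comfortable was at most 18% there. Protocol 12.13 gives 75 completers per arm and up to 120 enrolled.

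- q = 18%: 75 × 0.18 = 13.5, leaving 61.5; 120 × 0.18 = 21.6, leaving 98.4.
- At 75 per arm, for other assumed values: q = 9% gives 6.8; 30% gives 22.5; 50% gives 37.5; 60% gives 45.

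A majority cannot improve only if q is below 50%.

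**5. Illustrative power for the binary**

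Assume usual care stays at q and OSMT halves it, two-sided alpha 0.05, d = p1 − p2:

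power = Φ{[d − 1.96·√(2p̄(1−p̄)/n)] / √([p1(1−p1)+p2(1−p2)]/n)}

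- 18% to 9%, n = 75: p̄ = 0.135; (0.09 − 1.96 × 0.0558)/0.0553 = −0.35; power 36%.
- 18% to 9%, n = 120: (0.09 − 1.96 × 0.0441)/0.0437 = 0.08; power 53%.
- At n = 75: 9% to 4.5% gives 19%; 30% to 15% gives 60%; 50% to 25% gives 89%.

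Steps 4 and 5 apply to any yes/no comfort item, including a well-worded one. They show how much information the outcome can carry. They do not measure the loss caused by the wording, which depends on how often comfort is lost after being gained; the documents give no such rate.

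**The case against.** A reader might infer that change cannot be computed at all, that relapse is invisible, or that most participants cannot register any change. The documents do not support these readings.

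- The fourth choice on 7a is a current state, so a coarse binary exists at all three surveys.
- A participant comfortable at baseline can answer no on 7b, so loss by the end of the sessions is recorded. The gap is at six months.
- That most cannot improve is plausible but not established. The 18% comes from another sample and pools slow with never. This trial admits people from about six weeks after surgery, whose rate may be higher.

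Three further points count against the concern:

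- Both arms complete the same form at each survey, so a between-arm comparison at one survey is not biased by the change of form. This stands, but sensitivity at six months is still lost, and the movement from end of sessions to six months is distorted within each arm.
- Self-efficacy is a named secondary outcome, scored 1 to 10 at all three surveys, and includes confidence in managing ostomy care. Confidence is close to comfort but not the same, so this limits the damage without removing it.
- Items 7-28 of Appendix 2b are not readable in the copy reviewed, and both documents place comfort in the COH-QOL-CRC. A 0-10 comfort item given at all three surveys cannot be excluded. Against that, neighbouring entries in the same list match unscaled questions: clothing (2a Q4), diet (2a Q18-19) and care time (7a Q8).

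**Conclusion.** The concern holds in a limited form. In the readable forms, the planned comparison of change in comfort has no common scale except a binary that neither document defines. That binary takes past attainment for present comfort. It cannot validly show loss at six months among people comfortable at baseline, and the finer time categories do not measure benefit.

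The size in this trial is unknown. If q were 18%, the upper bound from the earlier study, 13.5 of 75 per arm could show improvement and 61.5 would depend on an item that cannot properly record loss at six months. A different q changes those counts in proportion.

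Comfort is neither the primary outcome nor, on the readable text, one of the listed secondary outcomes, and it carries no power claim. No conclusion about patient activation depends on it. The finding assumes that no scaled comfort item lies among the unreadable items of Appendix 2b.

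**What to change.** First check items 7-28 of Appendix 2b. If a scaled item on comfort with care exists, name it in 12.2 and the SAP as the comfort outcome; it is already collected at all three surveys.

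If not:

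1. Add question 6 of Appendix 7b (current comfort, yes/no) to Appendix 7a, so that it is asked at baseline and six months as well as after the sessions.
2. Name it in 12.2 and the SAP as the comfort outcome, compared between arms with adjustment for the baseline answer, for example by logistic regression on arm and baseline comfort.
3. Keep question 7 of Appendix 7a as a baseline descriptor only.
4. For participants already enrolled, prespecify still not comfortable against the rest as the baseline proxy, and state that it reflects past attainment.

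The cost is one extra question on one form and a short addition to the analysis text. The baseline remains imperfect for those already enrolled, and anyone who has also returned the old six-month form has only the same proxy there.

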 - i. Medication _____ Number of days used (0 to 7) _____
 - ii. Medication _____ Number of days used (0 to 7) _____
 - iii. Medication _____ Number of days used (0 to 7) _____

19. How much have you spent on purchases of ostomy appliances (including wafers and bags in total over the past 4 weeks)? \$0 \$1-\$25 \$26-50 \$51-100 \$100-\$150 \$150-\$200 \$200-\$250 over \$250

20. About how many times a day do you empty your drainable ostomy bag (or discard your closed/disposable bag)?

- None 1-4 5-8 More than 8

21. Over the past 4 weeks, what was the highest number of bag emptyings in a 24-hour period?

- None 1-4 5-8 More than 8

22. Over the past 4 weeks, what was the lowest number of bag emptyings in a 24-hour period?

- None 1-4 5-8 More than 8

23. How often do you typically discard a used bag and use a new bag?

- At every emptying Once a day Once every 2-3 days Less often

24. How much time does it usually take you to empty/dispose your bag?

- 1-5 minutes 5-10 minutes 10-15 minutes More than 15 minutes

25. How often do you typically change your wafer on a typical week? 1 2 3 4-7 More than 7

26. How much time does it usually take you to change your wafer and bag?

- 1-15 minutes 16-30 minutes 30-45 minutes 45-60 minutes More than 60 minutes

27. Do you usually receive help caring for your stoma and changing your ostomy appliance?

- a. No (skip to Question 27 below)
- b. Yes IF Yes, please check who your helper(s) is(are):
 Spouse/Significant Other Other family member Friend Home care nurse Other Paid Caregiver Other (please specify) _____

28. Has your bag leaked at any time over the past 4 weeks?

- a. No (skip to Question 28 below)
- b. Yes **IF YES**, how many times? 1-4 5-8 More than 8
- c. How many of these times involved a full spillage of your bag contents? 1-4 5-8
More than 8
- d. How much time does it require to clean up after a bag leak or spill? 1-30 minutes 31-60 mins.
More than 60 mins

29. Do you have waterproof covers on your mattress and primary chair(s)?

- a. No → Skip to Question 29 below.
- b. Yes **IF YES**, how much did you spend to purchase them?
\$0 \$1-\$10 \$11-\$25 \$26-\$50 \$51-\$75 \$76-\$100 \$101-\$150 \$151+

30. Do you have to make alterations to your clothing to accommodate your ostomy appliance?

- a. No **IF NO**, skip to Question 30 below.
- b. Yes **IF YES**, do you make these modifications yourself?
 - i. No
 - ii. Yes → **IF YES**, How much do you spend for these modifications?

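### The answer bands for daily ostomy care time overlap at 5, 10, 15 and 30 minutes, so a respondent at one of those times can change band with no change in time (minor)

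*Protocol*

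**What the plan says.** Protocol 8.2.1 to 8.2.3 schedule the full burden survey (Appendix 7a) at baseline and at 6 months, and the short one (Appendix 7b) at the end of sessions. Both ask for the average time that daily care takes; 7b words it as "On average, how long does it take to do your daily ostomy care". The answers printed in 7a item 8 are "0-5 min 5-10 min 10-15 min 15-30 min 30-60min More than 60min", and those in 7b item 7 are "0-5 min 5-10 min 10-15 min 15-30 min 30-60min More than 60 min". The question is therefore asked three times with the same bands.

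Other items on the forms are built in a similar way:
- 7a item 24, time to empty or dispose of the bag: "1-5 minutes 5-10 minutes 10-15 minutes More than 15 minutes".
- 7a item 26, time to change wafer and bag: "1-15 minutes 16-30 minutes 30-45 minutes 45-60 minutes More than 60 minutes". 7b item 10 uses the same bands.
- 7a item 19, spending on appliances, in its upper part: "51-100 \$100-\$150 \$150-\$200 \$200-\$250 over \$250".

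Protocol 12.2 and the SAP (Aim 1) list the responses whose change will be compared between arms, "including time taken to perform daily ostomy care". Protocol 12.5 adds time for bag and wafer management, and 12.4 adds out-of-pocket expenses for supplies.

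**The concern.** The bands are not mutually exclusive at values that people often give when asked for an average time. A participant who takes 10 minutes at every survey may tick 5-10 once and 10-15 the next time, and is then recorded as one band worse. The reverse is equally possible.

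If the choice is random, this adds noise to the change between surveys. The forms are self-completed by people who know whether they attended the sessions, so the choice could also lean differently in the two arms, and that would bias the comparison. Analysis cannot repair it afterwards, because a ticked 10-15 does not show whether the time was 10 or 12 minutes.

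**Working it through.** **Which values are shared.** The plan gives no figure to reproduce. Each whole minute or dollar was checked against the printed bands, with both ends of a range included and the top band read as strictly greater.

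| Item | Values with two valid answers | Boundaries not shared |
|---|---|---|
| 7a item 8, 7b item 7 | 5, 10, 15, 30 min | 60 |
| 7a item 24 | 5, 10 min | 15 |
| 7a item 26, 7b item 10 | 30, 45 min | 15/16, 60 |
| 7a item 19 | 100, 150, 200 dollars | 250 |

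The same form prints exclusive bands elsewhere: item 2g has 1-10, 11-30 and more than 30 minutes, and item 28d has 1-30, 31-60 and more than 60. Item 26 mixes both styles in one row. This points to a drafting slip rather than a convention.

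**One constant respondent.** Suppose the true time equals a shared value at two surveys and each choice is a coin toss. Then P(recorded better) = 0.5 × 0.5 = 0.25, P(recorded worse) = 0.25 and P(unchanged) = 0.50.

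**Assumptions for size.** None of these is in the documents except the numbers behind the arm size.
- Lognormal times with median 12 minutes and log-SD 0.8.
- Correlation 0.60 between surveys. Protocol 12.13 assumes this value for its own outcomes.
- 30% to 80% of answers rounded to common values.
- 120 × (1 − 0.15) = 102 per arm, from 12.13's maximum and dropout rate.
- A baseline-adjusted linear comparison of band number.

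**Answers affected.** With 60 not shared, about 32% to 62% of answers fall on a shared value. Of participants reporting the same minutes twice, 28% to 39% change band.

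**Random choice.** The false-positive rate stays near 5%. Power with exclusive against overlapping bands was 0.81/0.81, 0.82/0.81 and 0.81/0.78 at 30%, 50% and 80% rounding, a loss of 0 to 2.4 points. That run also allowed a free choice at 60. I repeated it with 60 not shared, 6,000 replicates, a log shift of −0.29, and answers rounded to 2, 5, 10, 15, 20, 30, 45, 60 or 90. The pairs were similar: 0.82/0.81, 0.81/0.80 and 0.81/0.78. The result depends on that rounding list. With 5 as the smallest rounded value (5, 10, 15, 20, 25, 30, 40, 45, 60, 75, 90, 120), 80% rounding gave 0.81/0.75, a loss of about 6 points.

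**Unequal choice at follow-up.** Spurious shift = share on a shared value × difference in choice probability. For 70% against 50% this is 0.32 × 0.20 = 0.06 to 0.62 × 0.20 = 0.12 band. Simulated false-positive rates at a nominal 5% (2,000 replicates, Monte Carlo error about 0.5 points):

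| Lower band chosen, OSMT vs UC | 102 per arm | 75 per arm (completion target in 12.13) |
|---|---|---|
| 55% vs 50% | 4.6-6.2% | not run |
| 60% vs 50% | 5.8-6.5% | 5.2-6.0% |
| 70% vs 50% | 7.0-12.5% | 6.2-11.0% |

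The ranges run over 30% to 80% rounding.

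**The case against.** The strongest reply is about weight. PAM is the primary outcome; self-efficacy, the COH-QOL-CRC scales and ostomy knowledge are the listed secondary outcomes. The endpoint table in section 11.0 does not name daily care time. Protocol 12.2 and the SAP mention it in an unranked list, and they attribute it to the COH-QOL-CRC. Linking it to 7a item 8 and 7b item 7 is an inference, though a natural one because those items ask exactly that question. No sample size or power claim depends on these items. All of this stands, and it is why the point is minor.

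The forms also ask only for best estimates, in coarse bands, with the same wording in both arms. The expected effect is then non-differential noise. That stands too, as long as the choice of band does not differ by arm.

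A reader might infer more: that the overlap will produce a false arm difference. The documents do not support that. Nothing in them suggests that OSMT participants would choose differently from UC participants, or by how much. The upper figure of 12.5% needs both a 20-point tilt and 80% of answers rounded. Self-report by people who know their arm could favour OSMT under exclusive bands as well; the overlap only widens the room for it.

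A reader might also take 60 minutes as shared, or every boundary in the other items. The table of values shows otherwise.

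The callback rule in 8.2.9 mentions double-marked answers alongside missing ones. It does not tell a respondent which single band to tick, so it does not remove the ambiguity.

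**Conclusion.** The overlap is certain; it can be read from the forms. It affects 5, 10, 15 and 30 minutes in the daily care time item on both forms, and some boundaries in 7a items 19, 24 and 26 and 7b item 10. It touches the comparison of change in daily care time and the Aim 2 time and expense measures. It does not touch the conclusion on PAM or on the listed secondary outcomes.

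The size is conditional on assumed care times and rounding. Under random choice it is modest noise: about 0 to 2 power points in the base case, about 6 with the coarser rounding tried. Bias arises only if the arms choose differently, and the false-positive rates for that case illustrate hypothetical tilts and predict nothing. Severity is minor.

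**What to change.** Print exclusive bands, identical in 7a and 7b where the item appears in both:
- 7a item 8 and 7b item 7: 0-5, 6-10, 11-15, 16-30, 31-60, more than 60 minutes.
- 7a item 24: 1-5, 6-10, 11-15, more than 15 minutes.
- 7a item 26 and 7b item 10: 1-15, 16-30, 31-45, 46-60, more than 60 minutes.
- 7a item 19, upper part: 51-100, 101-150, 151-200, 201-250, over 250 dollars.

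Before enrolment this costs a wording edit to two forms and their web versions, with no added items.

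If enrolment has begun, switching everyone at once would break the change score of each participant who straddles the two versions, and that could cost more than the noise removed. Give the new version only to newly enrolled participants, at all their time points, keep those already enrolled on the old version, and record a form-version flag for the analysis. The overlap then remains in the data of those already enrolled and should be reported as a limitation of these items.
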